11. SELECTION AND WITHDRAWAL OF PATIENTS, COHORTS **2 AND 3**

11.1. Patient Inclusion Criteria, Cohort 2

Individuals of either gender or any race will be eligible for study participation in Cohort 2 if they:

- 1. Are male or female between 18 and 85 years of age.
- 2. Have a diagnosis of bilateral ocular hypertension or primary open-angle glaucoma.
- 3. Normal appearing anterior chamber angles (Shaffer classification Grade 3 or 4, with an angle of at least 20° determined by gonioscopy, and confirmed to have an open angle as determined by anterior chamber OCT evaluated by a central reading center prior to dosing).
- 4. Are currently treated with topical PGA for ocular hypertension in both eyes.
- 5. Patients who in the opinion of the investigator: have an IOP in both eyes that is considered to be adequately controlled at the Screening Visit (Visit 1); can be safely withdrawn from IOP medications in both eyes during the washout period, and who are not considered to be at significant risk for disease progression throughout the trial.
- 6. At the Baseline Visit after washout (Visit 2), have IOP measurements that meet all of the following:
 - a. Have an IOP at 8:00 a.m. (±30 minutes) and at 10:00 a.m. (±30 minutes) between 22 and 34 mm Hg in both eves with a <4 mm Hg difference between the eves
 - b. Have an IOP at 4:00 p.m. (±30 minutes) between 19 and 30 mm Hg in both eyes with a ≤4 mm Hg difference between each eye
- 7. At the Dosing Visit (Visit 3), have IOP measurement that is between 22 and 34 mm Hg in both eyes with a ≤ 4 mm Hg difference between the eyes.
- 8. Have endothelial cell counts of at least 2000 cells/mm² and normal endothelial cell morphology prior to dosing as evaluated by central reading center.
- 9. If female, patients must be incapable of pregnancy because of hysterectomy, tubal ligation or have been amenorrheic for at least 2 years. Female patients much have a negative pregnancy test and not be nursing. If female patient is capable of pregnancy, she must use effective (e.g. double barrier) method of birth control for the duration of the study.
- 10. Must be able to provide a written informed consent to participate in the study, in accordance with the international Conference on Harmonization (ICH) Good Clinical Practice (GCP) guidelines, and local regulations, before initiating any study-related procedures.

11.2. Patient Exclusion Criteria, Cohort 2

Individuals of either gender or any race will not be eligible for study participation in Cohorts 2 if they:

- 1. Are diagnosed with closed angle glaucoma, exfoliation syndrome or exfoliation glaucoma, pigment dispersion or secondary glaucoma.
- 2. Are insufficiently responsive to PGA topical treatment, i.e., are PGA non-responders.
- 3. Have a history of glaucoma-related surgery (e.g., trabeculectomy, cryotherapy, laser iridotomy and minimally invasive procedures including shunts/stents).
- 4. Have severe glaucoma with a mean defect (MD) worse than -8.0, a central island of vision, or otherwise severe glaucoma that would not tolerate a short-term increase in IOP.
- 5. According to the investigator's best judgment, are at risk for progression of glaucoma, VF or VA worsening as a consequence of participation in the trial.
- 6. Have any abnormality preventing reliable applanation tonometry in either eye.
- 7. Have a central corneal thickness less than 500 micrometers or greater than 600 micrometers as determined by pachymetry at the Screening Visit (Visit 1).
- 8. Have a history of recurrent corneal erosion syndrome, multiple corneal abrasions, or an abrasion that was slow to heal
- 9. Have had intraocular conventional surgery, intraocular laser surgery, corneal refractive surgery or eyelids surgery within the past 3 months. Complicated cataract surgery that resulted in intraocular lens placement outside the capsular bag or a break in the posterior capsule is not allowed.
- 10. Are currently diagnosed with active infectious/noninfectious conjunctivitis, or moderate to severe blepharitis in either eye. (Chronic mild blepharitis or injection related to mild blepharitis, lid lag, mild dry eye or seasonal allergies are allowed.)
- 11. Are currently taking or have taken corticosteroids (oral, ocular, injectable, IV) or used dermatology formulations of steroids in the vicinity of eyes in the 1 month prior to Visit 1; have a history of chronic ocular corticosteroid (topical or intraocular) use within the past year. Inhaled, intranasal, or topical (dermal) steroids not in the vicinity of the eyes is permissible if on a stable dose for at least 1 month prior to Visit 1.
- 12. Have any media opacity or are uncooperative in such a way that restricts adequate examination of the ocular fundus or anterior chamber in either eye.
- 13. Are unwilling to discontinue use of contact lenses for the duration of their study participation.
- 14. Have progressive retinal or optic nerve disease apart from glaucoma or history of uveitis or keratitis.

- 15. Have any history of allergic hypersensitivity or poor tolerance to any components of the preparations used in this trial such as travoprost or poly-lactic acid or similar excipients, topical anesthetic (proparacaine 0.5% or equivalent), iodine, timolol maleate and VIGAMOX® (or generic equivalent).
- 16. Have a requirement for any ocular medications that are specifically disallowed in this protocol for any condition during the study or within the specified timeframe prior to Visit 2.
- 17. Have a history, or a suspected history of drug or alcohol dependence in the preceding year.
- 18. Currently using or used marijuana in the past 30 days prior to Visit 1.
- 19. Have received any investigational product within the past 30 days prior to Visit 1.
- 20. Are an employee of the clinical site that is directly involved in the management, administration, or support of this study or are an immediate family member of the same
- 21. Patients who, per investigator's judgment, are not good clinical trial candidates due to personal (e.g., perceived willingness or ability to comply with protocol, significant traveling distance to medical center) and/or medical (i.e. mental illness, other non-ocular medical conditions, or laboratory abnormalities that might negatively impact trial participation or outcome) conditions that would likely impede the patient's successful study completion or planned analyses.

11.3. Patient Inclusion Criteria, Cohort 3

Individuals of either gender or any race will be eligible for study participation in Cohort 3 if they:

- 1. Are male or female between 18 and 85 years of age.
- 2. Have a diagnosis of bilateral ocular hypertension or primary open-angle.
- 3. Normal appearing anterior chamber angles (Shaffer classification Grade 3 or 4, with an angle of at least 20° determined by gonioscopy, and confirmed to have an open angle as determined by anterior chamber OCT evaluated by a central reading center prior to dosing in the study eye).
- 4. Are currently treated with topical PGA for ocular hypertension in both eyes. (Dual therapy (i.e. PGA and another IOP lowering agent) is acceptable)
- 5. In the opinion of the investigator, the non-study eye can be adequately controlled with timolol maleate 0.5% ophthalmic solution BID.
- 6. Patients who in the opinion of the investigator, have an IOP in both eyes that is considered to be adequately controlled at Screening (Visit 1), can be safely withdrawn from IOP medications in both eyes during the washout period, and who are not considered to be at significant risk for disease progression throughout the trial.

- 7. At Baseline (Visit 2) after washout, have IOP measurements that meet all of the following:
 - a. Have an IOP at 8:00 a.m. (±30 minutes) and at 10:00 a.m. (±30 minutes) between 22 and 34 mm Hg in both eyes with a ≤4 mm Hg difference between the eyes
 - b. Have an IOP at 4:00 p.m. (± 30 minutes) between 19 and 30 mm Hg in both eyes with a ≤ 4 mm Hg difference between each eye
 - c. Demonstrate an 8 AM IOP increase of at least 4 mmHg in each eye Baseline (Visit 2) compared to the Screening (Visit 1) IOP measurements.
- 8. At Dosing (Visit 3), have IOP measurement that is between 22 and 34 mm Hg in both eyes with a ≤4 mm Hg difference between the eyes.
- 9. Have endothelial cell counts of at least 2000 cells/mm² and normal endothelial cell morphology at Screening (Visit 1) as evaluated by central reading center in the study eye.
- 10. If female, patients must either be incapable of pregnancy because of hysterectomy, tubal ligation or have been amenorrheic for at least 2 years or must use effective (e.g., double barrier) method of birth control for the duration of the study. Female patients must have a negative pregnancy test, and not be nursing
- 11. Must be able to provide a written informed consent to participate in the study, in accordance with the international Conference on Harmonization (ICH) Good Clinical Practice (GCP) guidelines, and local regulations, before initiating any study-related procedures.

11.4. Patient Exclusion Criteria, Cohort 3

Individuals of either gender or any race will not be eligible for study participation in Cohort 3 if they:

- 1. Are diagnosed with closed angle glaucoma, exfoliation syndrome or exfoliation glaucoma, pigment dispersion or secondary glaucoma in either eye.
- 2. Are insufficiently responsive to PGA topical treatment, i.e., are PGA non-responders in either eye.
- 3. Have a history of glaucoma-related surgery (e.g., Selective Laser Trabeculoplasty (SLT), Argon Laser Trabeculoplasty (ALT), trabeculectomy, cryotherapy, laser iridotomy and minimally invasive procedures including shunts/stents) in the study eye.
- 4. Have severe glaucoma with a mean defect (MD) worse than -8.0, a central island of vision, or otherwise severe glaucoma that would not tolerate a short-term increase in IOP including advanced cupping in either eye.
- 5. Have manifest refraction BCVA worse than 20/80 Snellen in either eye as measured using an ETDRS chart in.
- 6. Have hyperemia score of 1 or greater at Baseline (Visit 2).

- 7. According to the investigator's best judgment, are at risk for progression of glaucoma, VF or VA worsening as a consequence of participation in the trial in either eye.
- 8. Have any abnormality preventing reliable applanation tonometry in either eye.
- 9. Have a central corneal thickness less than 500 micrometers or greater than 600 micrometers as determined by pachymetry at Screening (Visit 1) in either eye.
- 10. Have a history of recurrent corneal erosion syndrome, multiple corneal abrasions, or an abrasion that was slow to heal in either eye.
- 11. Have had intraocular conventional surgery, intraocular laser surgery, corneal refractive surgery or eyelids surgery within the past 3 months in the study eye. Complicated cataract surgery that resulted in intraocular lens placement outside the capsular bag or a break in the posterior capsule in the study eye is not allowed.
- 12. Are currently diagnosed with active infectious/noninfectious conjunctivitis, or moderate to severe blepharitis in either eye. (Chronic mild blepharitis or injection related to mild blepharitis, lid lag, mild dry eye or seasonal allergies are allowed.)
- 13. Are currently taking or have taken corticosteroids (oral, ocular, injectable, IV) or used dermatology formulations of steroids in the vicinity of eyes in the 1 month prior to Screening (Visit 1); have a history of chronic ocular corticosteroid (topical or intraocular) use within the past year. Inhaled, intranasal, or topical (dermal) steroids not in the vicinity of either eye is permissible if on a stable dose for at least 1 month prior to Screening (Visit 1).
- 14. Have any medial opacity or are uncooperative in such a way that restricts adequate examination of the ocular fundus or anterior chamber in either eye.
- 15. Are unwilling to discontinue use of contact lenses for the duration of their study participation.
- 16. Have progressive retinal or optic nerve disease apart from glaucoma or history of uveitis or keratitis in either eye.
- 17. Have any history of allergic hypersensitivity or poor tolerance to any components of the preparations used in this trial such as travoprost or poly-lactic acid or similar excipients, topical anesthetic (proparacaine 0.5% or equivalent), iodine, timolol maleate, and VIGAMOX® (or generic equivalent).
- 18. Have a requirement for any ocular medications that are specifically disallowed in this protocol for any condition during the study or within the specified timeframe prior to Baseline (Visit 2).
- 19. Have a history, or a suspected history of illicit drug or alcohol dependence in the preceding year.
- 20. Currently using or used marijuana in the past 30 days prior to Screening (Visit 1).

21. Have received any investigational product within the past 30 days prior to Screening (Visit 1) or have ever been previously implanted in the anterior segment with experimental therapies.

- 22. Are an employee of the clinical site that is directly involved in the management, administration, or support of this study or are an immediate family member of the same
- 23. Patients who, per investigator's judgment, are not good clinical trial candidates due to personal (e.g., perceived willingness or ability to comply with protocol, significant traveling distance to medical center) and/or medical (e.g., mental illness, other non-ocular medical conditions, or laboratory abnormalities that might negatively impact trial participation or outcome) conditions that would likely impede the patient's successful study completion or planned analyses.

11.5. Dosing Criteria, Cohorts 2 and 3

At the Dosing Visit (Visit 3/Day 1), an eligible patient must:

• Continue to meet all inclusion/exclusion criteria as defined in Section 11.1, Section 11.2, Section 11.3, and Section 11.4 depending on cohort.

11.6. Patient Rescue Criteria, Cohorts 2 and 3

For Cohort 2 and its Extensions 1 and 2, rescue therapy may be allowed in the study eye if in the opinion of the investigator the IOP is not well controlled on any two visits after Day 1 that are separated by at least 4 weeks. If IOP is well controlled, rescue therapy should be discontinued and the patient should resume regular study visit schedule. Each patient can be subjected to up to two rescue treatments. If rescue therapy is needed after 2 prior rescue therapy periods or after 7 months post-dose, the patient should be permanently rescued until the completion of the study.

For Cohort 2 and its Extensions 1 and 2, AZOPT® (brinzolamide ophthalmic suspension) 1% will be used for rescue therapy. Patients will be given four weeks of AZOPT treatment 3 times daily and evaluated at their next study visit. If IOP is well controlled, rescue therapy should be discontinued and patients should resume the regular study visit schedule per protocol. At the investigator's discretion, the patient can be brought in for an unscheduled visit two weeks following the discontinuation of AZOPT for an IOP assessment. The investigator can choose to measure IOP at 8 AM or full diurnal. If the IOP is well controlled during the unscheduled visit, the patient should resume the regular study visit schedule. If the patient's IOP is not well controlled during the unscheduled visit, the patient should be permanently rescued with Timolol maleate 0.5% ophthalmic solution twice a day until the completion of the study. Thus, each patient can be subjected to only one AZOPT rescue treatment. Notwithstanding the above, both the study and non-study eyes may be rescued at any time, at the investigator's discretion, if it is considered to be in the best interest of the patient.

For Cohort 3 and its Extension 1, rescue therapy may be allowed in the study eye if, in the opinion of the investigator, the IOP is not well controlled on any two visits after Month 3 (Day 84) that are separated by at least 4 weeks (+/- 7 days). Timolol maleate 0.5% ophthalmic

solution administered BID daily will be used for rescue therapy. The patient should be permanently rescued with Timolol maleate 0.5% ophthalmic solution twice a day until the completion of the study. Notwithstanding the above, both the study and non-study eyes may be rescued at any time, at the investigator's discretion, if it is considered to be in the best interest of the patient.

11.7. Patient Withdrawal Criteria, Cohorts 2 and 3

Any patient who wishes to withdraw from the study on his or her own accord for any reason is entitled to do so without obligation. Patients who are withdrawn from the study prior to dosing will be replaced. Any patient may be removed from the study by the investigator if it is deemed necessary for the patient's safety.

In the event that withdrawal of a dosed patient is medically necessary or requested by the patient, the investigator should make every attempt to complete all assessments indicated at the Early Exit/Exit (Visit 16 for Cohorts 2 and 3, Visit 22 for Cohort 2 Extension 1, Visit 25 for Cohort 2 Extension 2; and Visit 22 for Cohort 3 Extension 1).

If patient withdrawal is required due to a treatment related AE or SAE and the implant removal is necessary prior to its biodissolution, the removal of the ENV515-3 or ENV515-3-2 implant(s) should occur as soon as possible based on the judgment of the investigator and safety of the patient.

If an treatment related AE or SAE is unresolved at the time of the patient's final study visit, an effort will be made to follow the patient until the AE or SAE is resolved or stabilized (Section 17), the patient is lost to follow-up, or there is some other resolution of the event. The investigator should make every attempt to follow all SAEs to resolution.

Following ongoing review of the data by the medical monitor, any individual patient safety concerns will be discussed between Envisia representative and investigator. If the investigator determines that a patient should be discontinued and withdrawn from the study, the removal of the ENV515 implants should occur as soon as possible based on the judgment of the investigator.

A patient may be discontinued and withdrawn from the study at any time at the discretion of the investigator for any safety reason, including but not limited to those listed below:

- IOP measurement of 35 mm Hg or greater in either eye at any measurement
- Any clinically significant pole changes, including but not limited to:
 - Progressive VF loss or optic nerve changes
 - CME
 - Other significant disease such as AMD or vascular occlusion
- Pachymetry measurement of the central corneal thickness which reveals a change that falls outside of the normal variability when compared to the baseline measurement

- An acute increase of 15% or greater in corneal thickness for a period of <24 hours after the instillation of study drug
- A chronic increase of 10% or greater in corneal thickness for a period of
 24 hours after the instillation of study drug
- A ≥30% decrease in central endothelial cell density as evaluated by the centralized reading center

In the event that study discontinuation and withdrawal of a subject is necessary, the investigator should make every attempt to complete all protocol safety assessments and visits. Unless consent has been withdrawn, any subject is considered to be in the treatment phase of the study until the completion of the study, and such subjects should continue to be followed and will be expected to complete all safety assessments and visits.

11.8. Early Exit Criteria, Cohorts 2 and 3

Patients may also exit the study sooner than their exit visit if all of the following are true:

- They have received rescue therapy
- Their IOP in the study eye is well controlled
- No implant remnants are visible by gonioscopy on two consecutive visits
- No treatment related adverse events are present that require continued monitoring.

Communication

12. PROCEDURE SCHEDULE BY STUDY VISIT, COHORT 2

12.1. Visit 1/-49 to -29 days/Screening Evaluation, Cohort 2

At Visit 1, patients will be screened, and if eligible, enrolled into the study. Before any study specific assessments are performed, written informed consent will be obtained from each patient. Screening procedures can be conducted over several visits but should be completed within a 7 day period. During the visit, the procedures described below will be performed.

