Structure: The Cohort 2 phase of the Phase 2a clinical study is an up to 12-month, prospective, open-label, active-comparator-controlled, multi-center study of ENV515-3 (travoprost) Intracameral Implant. While the Cohort 1 enrolled glaucoma patients scheduled for cataract removal and the ENV515 implants were removed after 28 days during the cataract procedure, the Cohort 2 phase of the study will enroll glaucoma patients without the need for cataract surgery in order to study ENV515 over its entire duration of IOP-lowering efficacy, or up to 12 months after the first dose.

Duration of Patient Participation: Approximately a maximum of 14 months including up to a 49 day washout period, implantation/treatment administration day, 3 month primary efficacy and safety evaluation period post initial dose of ENV515 in the study eye, and a follow-up for 9 months after the 3 month primary efficacy and safety evaluation period

Study Treatment Investigational Product: ENV515-3 (travoprost) Intracameral Implant

Reference Product: Timolol maleate 0.5% ophthalmic solution administered BID daily in the non-study eye

Dosage/Dose Regimen/Treatment Groups:

ENV515-3 Group: Two ENV515-3 (travoprost) implants/eye administered into the study eye as a single, unilateral dose via intracameral injection on Day 1

Control Group: Timolol maleate 0.5% ophthalmic solution administered BID daily in the non-study eye

Rescue Therapy: Rescue therapy may be allowed in the study eye for a change from baseline in IOP of <20% on any two visits after Day 1 separated by at least 4 weeks. Both the study and non-study eyes may be treated at any time, at the investigator's discretion, if it is considered to be in the best interest of the patient.

Randomization/Stratification: No randomization is required as this is an open-label, single arm study.

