Structure: The Cohort 2 study Extension 1 will extend the ongoing 12 month Cohort 2 by 6 months for a total of 18 months duration for up to 5 patients dosed with a single low dose of ENV515-3 in Cohort 2. The original Cohort 2 of the Phase 2a clinical study was up to 12-month, prospective, open-label, active-comparator-controlled, multicenter study of ENV515-3 (travoprost) Intracameral Implants. The Cohort 2 phase of the study enrolled glaucoma patients to study ENV515 over its entire duration of IOP-lowering efficacy, or up to 12 months after the first dose.

Duration of Patient Participation including study Extension 1: Approximately a maximum of 20 months including up to a 49 day washout period, implantation/treatment administration day, 3 month primary efficacy and safety evaluation period post initial dose of ENV515 in the study eye, a follow-up for 9 months, and 6 month study Extension 1

Study Treatment Investigational Product: ENV515-3 (travoprost) Intracameral Implant

Reference Product: Timolol maleate 0.5% ophthalmic solution administered BID daily in the non-study eye

Dosage/Dose Regimen/Treatment Groups:

ENV515-3 Group: Two ENV515-3 (travoprost) implants/eye administered into the study eye as a single, unilateral dose via intracameral injection on Day 1

Control Group: Timolol maleate 0.5% ophthalmic solution administered BID daily in the non-study eye

Rescue Therapy: Rescue therapy may be allowed in the study eye for a change from baseline in IOP of <20% on any two visits after Day 1 separated by at least 4 weeks. Both the study and non-study eyes may be treated at any time, at the investigator's discretion, if it is considered to be in the best interest of the patient.

Randomization/Stratification: No randomization is required as this is an open-label, single arm study extension for up to 5 patients who had been dosed in ENV515-01 Cohort 2 study.

Cohort 2 Study Extension 1 Visit Schedule: Visit schedule encompasses Treatment Visits 17 to 21 (Month 13 and every month thereafter to Month 17) and Exit Visit 22 (Month 18). Patients may be exited sooner than Month 18 if they have received rescue therapy, their IOP in the study eye is well-controlled, no implant remnants are visible by gonioscopy during two consecutive visits, and no treatment related adverse events (AEs) are present that require continued monitoring.

Response Measures in Cohort 2 Study Extension 1 (Month 12 to 18):

Exploratory Efficacy Measure:

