Duration of Patient Participation: Approximately 14 months including washout of current PGA therapy, implantation/treatment of investigational product, 3-month primary efficacy and safety evaluation period post dose of ENV515 in the study eye, and followed for an additional 9 months of safety follow-up.

Study Treatment Investigational Product: one or two implant(s) per eye of ENV515-3-2 (travoprost) Intracameral Implant

Reference Product: Timolol maleate 0.5% ophthalmic solution administered BID daily in the non-study eye

Dosage/Dose Regimen/Treatment Groups:

- ENV515-3-2 Low Dose Group: One ENV515-3-2 (travoprost) implant administered into the study eye as a single, unilateral dose via intracameral injection on Day 1
- ENV515-3-2 High Dose Group: Two ENV515-3-2 (travoprost) implants administered into the study eye as a single, unilateral dose via intracameral injection on Day 1
- Control Group: Timolol maleate 0.5% ophthalmic solution administered BID daily in the non-study eye

Rescue Therapy: Rescue therapy may be allowed in the study eye if, in the opinion of the investigator, the IOP is not well controlled on any two visits after Month 3 (Day 84) that are separated by at least 4 weeks (+/- 7 days). Timolol

maleate 0.5% ophthalmic solution administered BID daily will be used for rescue therapy. The patient should be permanently rescued with Timolol maleate 0.5% ophthalmic solution twice a day until the completion of the study. Notwithstanding the above, both the study and non-study eyes may be rescued at any time, at the investigator's discretion, if it is considered to be in the best interest of the patient.

Randomization/Stratification: No randomization is conducted as this is an open-label study.

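### The only planned IOP table for Cohorts 2 and 3 does not separate readings taken on or after rescue, so rescue-drug effect could hide loss of implant effect; the Cohort 2 rescue text also conflicts

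*Protocol*

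**What the plan says.** **Analysis.** SAP section 8.1 for Cohorts 2 and 3 summarises IOP and change from baseline by visit and time, cohort dose group and eye. Section 4 uses the safety population throughout. Table 14.2.1 is the only efficacy table in section 11, and section 10 drops the secondary summaries and all formal testing. Rescue is not mentioned anywhere in this SAP: there is no exclusion, flag or separate presentation. Protocol 18.4 says only that missing, unused or spurious data will be noted.

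**Rescue, Cohort 3.** Protocol 11.6: "For Cohort 3 and its Extension 1, rescue therapy may be allowed in the study eye if, in the opinion of the investigator", IOP is poorly controlled at two visits after Month 3 at least four weeks apart. Then: "The patient should be permanently rescued with Timolol maleate 0.5% ophthalmic solution twice a day until the completion of the study".

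**Rescue, Cohort 2.** The Cohort 2 synopsis, repeated for both extensions, sets the trigger as a "change from baseline in IOP of <20% on any two visits after Day 1", at least four weeks apart. Protocol 11.6 instead says "rescue therapy may be allowed in the study eye if in the opinion of the investigator the IOP is not well controlled". On number, 11.6 first says "Each patient can be subjected to up to two rescue treatments" and makes rescue permanent "If rescue therapy is needed after 2 prior rescue therapy periods or after 7 months post-dose". Its next paragraph gives a four-week AZOPT (brinzolamide) course, then permanent timolol if control fails after the course is stopped, and concludes: "Thus, each patient can be subjected to only one AZOPT rescue treatment".

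**Both cohorts.** Either eye may be rescued at any time at the investigator's discretion. Protocol 11.8 allows early exit only when four conditions all hold, one being prior rescue. Other rescued patients keep attending visits and having IOP measured.

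**The concern.** Duration of effect is a stated question. The Cohort 2 extension hypotheses are that the IOP effect of a single dose will end between 13 and 18 months (Extension 1) or 13 and 21 months (Extension 2). SAP section 2 describes Cohort 2 as assessing how long IOP lowering lasts. Rescue is given because control is failing. An unflagged study-eye mean that includes rescued eyes therefore adds a second drug's effect at just the time when the implant's effect may be ending, and waning can look like stability or improvement.

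In Cohort 3 the rescue drug is timolol, which is also the fellow eye's assigned treatment. After rescue, an eye in the implant column is on implant plus timolol, compared with timolol alone. The fellow-eye column has the same gap, because fellow eyes may also be rescued.

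Rescue is plausible. In Cohort 1 the same 28.2 µg dose gave a mean reduction of 21.3% (SD 8.3) at Day 25 (Protocol 1.4.2), which is close to the 20% trigger in the Cohort 2 synopses.

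**Working it through.** The plan gives no figure on this point to reproduce. The check covers which visits can be affected and how far one rescued eye would move a mean.

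**1. Do post-rescue values enter the table?** Rescued patients stay on schedule (11.6) unless all the early-exit conditions hold (11.8). The SAP summarises every safety-population patient by visit and eye. So yes, if any eye was rescued.

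**2. Which visits?**
- *Any-time override:* any post-dose visit, in either cohort.
- *Cohort 2, two-visit rule, nominal days:* Days 2 and 28 are 28 − 2 = 26 days apart, which is too short. Days 14 and 42 are 42 − 14 = 28 days apart, which qualifies. Rescue could start at Day 42, so Day 84, a primary visit, is at risk.
- *Cohort 2, using visit windows:* Visit 4 on Day 2 and Visit 5a on Day 30 or 31 are 28 or 29 days apart. Rescue could start then, so the Day 42 primary visit is also at risk.
- *On or off drug at Day 84:* a four-week course from Day 42 ends at Day 42 + 28 = Day 70, 14 days before Day 84. Section 11.6 does not say whether drops continue to the visit. This is why values after a stopped course need their own flag.
- *Cohort 3:* 11.6 needs two visits after Day 84, hence Months 4 and 5, with Month 6 (Visit 10) the first affected. The rescue row of Table 5, however, is marked for eligible patients from Visit 7 (Day 84). A Table 5 footnote allows rescue only after that visit's IOP readings, so a Visit 7 rescue would first affect Visit 8.

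**3. Size.** For k rescued eyes, added lowering e and n eyes measured, the shift in the visit mean is k × e / n. The dosed numbers are n = 5 (Protocol 1.3), n = 6 low dose and n = 9 high dose (Protocol 10.4). The documents do not give e; 2 to 5 mmHg is assumed. For k = 1:

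| Group | n | e = 2 | e = 5 |
|---|---|---|---|
| Cohort 2 | 5 | 0.40 | 1.00 |
| Cohort 3 low | 6 | 0.33 | 0.83 |
| Cohort 3 high | 9 | 0.22 | 0.56 |

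For scale, the Cohort 1 mean change at 28.2 µg was −5.1 mmHg, so the Cohort 2 shift is 0.40/5.1 to 1.00/5.1, about 8% to 20% of it. Late visits have fewer eyes, because extensions are optional and rescued patients may exit, and the shift then grows. With four eyes it would be 2/4 = 0.50 to 5/4 = 1.25.

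**4. Why neither version suffices alone.** Take four eyes at −6 mmHg and one that has waned to −3 (assumed values).
- No rescue: (4 × −6 − 3)/5 = −5.4.
- Rescue adds 4 mmHg to the waned eye, all values kept: (4 × −6 − 7)/5 = −6.2.
- Rescued eye dropped: −6.0.

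Both summaries look better than −5.4. In general, dropping an eye that sits d mmHg above the rest flatters the mean by d/n (here 3/5 = 0.6).

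**5. The Cohort 2 text.** Reading two treatments as one AZOPT course plus timolol does not reconcile 11.6. Its first paragraph makes rescue permanent only after two earlier periods or after seven months; its second allows one temporary course.

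**The case against.** The strongest reply is that this is a descriptive table in an abbreviated report, written because the IND is being withdrawn. The stated objective of Cohorts 2 and 3 is safety and tolerability, Cohort 3 lists no efficacy measure, and nothing is tested. Summarising all values is a legitimate choice. With 20 patients, the IOP and concomitant medication listings let a reader trace rescue by hand.

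Much of this stands. No error rate is affected, and an all-values table is worth keeping. But the SAP does not say that it chose to include post-rescue values, and the table would not show which means contain them. Hand tracing also needs the eye and the indication, because timolol is both the fellow eye's treatment and a study-eye rescue drug. The medication fields in Protocol 16.2.1 include indication and dates but do not name the eye.

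It is also fair that the text conflict changes little. Every version makes rescue discretionary and adds the any-time override. Protocol 1.2 calls Cohort 2 both ongoing and completed, so rewriting its rule may change no treatment decision.

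Three stronger readings are tempting and not supported. A reader might infer that the IOP means are in fact contaminated; the documents do not say that any eye was rescued. A reader might infer a fixed list of affected visits from the two-visit rule; the override, the visit windows and the Table 5 row prevent that. A reader might infer that the conflicting triggers led sites to treat patients differently; nothing shows this.

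**Conclusion.** The reporting gap is real and should be closed. Followed as written, the SAP puts any post-rescue IOP into the same column as unrescued values in its only efficacy table, where it can mask the waning that the Cohort 2 extensions set out to detect. The consequence depends on at least one eye having been rescued.

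The sizes in the table above are illustrations. They rest on an assumed rescue effect of 2 to 5 mmHg, one rescued eye and all dosed patients still measured. Any post-dose visit can be affected through the override. Under the two-visit rule, exposure in Cohort 2 can begin after about Day 30 to 42. In Cohort 3 the text implies rescue no earlier than Month 5, while Table 5 suggests it may be possible from Day 84.

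The Cohort 2 conflict on trigger and number of rescues is genuine but secondary and mainly editorial.

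**What to change.** For both cohorts:

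1. List each rescue with eye, drug, start and stop dates, and reason.
2. In Listing 16.2.1, flag each IOP value as before rescue, on rescue, or after a stopped course. Readings taken before the first rescue dose at the rescue visit count as before, in line with the Table 5 footnote.
3. In Table 14.2.1, show the number rescued per dose group and eye at each visit.
4. Add a pre-rescue-only version of Table 14.2.1 beside the all-values version.

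For Cohort 2, state in the CSR which trigger and which limit on rescues the sites applied. If the protocol text is corrected as well, keep one trigger and one limit.

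The cost is one short listing, one flag, added counts and one repeat table for 20 patients. Drug, dates and indication are already recorded; the eye may have to be taken from the patient chart. The drawback is that the pre-rescue version drops poorly controlled eyes and can flatter the implant at late visits, so the two versions and the rescue counts must be read together.
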